4.2.2 Post Treatment response at 2-3 months after RT

A complete response will be defined as resolution of all disease in the head and neck by CT at 2 months or PET/CT at 3 months. On CT scan, nodes less than 1 cm in short axis without evidence of necrosis will be defined as negative. On PET/CT, resolution of hypermetabolism to maximum SUV of 3 or less will be defined as negative, even with evidence of a node larger than 1 cm in short axis on CT scan. CT scans or PET scans which do not meet these criteria will be reviewed at the Moffitt H&N tumor board for determination of response.

# 5 STUDY ENROLLMENT AND WITHDRAWAL

Men and women of all races and ethnic groups are eligible for this trial.

#### 5.1 PARTICIPANT INCLUSION CRITERIA

In order to be eligible to participate in this study, an individual must meet all of the following criteria:

- Provision of signed and dated informed consent form
- Stated willingness to comply with all study procedures and availability for the duration of the study
- Male or female, aged  $\geq$  18 years
- Pathologically (histologically or cytologically) proven diagnosis of p16+ or HPV+ squamous cell carcinoma (including the histological variants papillary squamous cell carcinoma and basaloid squamous cell carcinoma) of the oropharynx; cytologic diagnosis from a cervical lymph node is sufficient. Patients with unknown primary (T0) should be both p16 and HPV positive. Clinical evidence should be documented, and may consist of pathology, palpation, imaging, or endoscopic evaluation, and should be sufficient to estimate the size of the primary (for T stage).
- AJCC 8th edition staging T0-2 N0-1 M0 (N1 includes clinical tumor involvement in only 1-5 lymph nodes) Patients with any smoking history are included if N0 or a single involved node size ≤3cm. However, if the number of involved lymph node is ≥2 or any lymph node size >3 cm, only patients with ≤ 10 pack years of smoking is eligible.
- Patients must have clinically or radiographically evident measurable disease at the primary site or at nodal stations.
- CT or MRI performed at least 1 week apart. This can consist of diagnostic imaging and radiation therapy planning imaging.
- No evidence of distant metastases
- ECOG Performance Status 0 to 2

#### 5.2 PARTICIPANT EXCLUSION CRITERIA

An individual who meets any of the following criteria will be excluded from participation in this study:

- Age < 18
- Positive urine pregnancy test
- Evidence of distant metastases
- Patients with >10 pack years of smoking is excluded if the number of involved lymph node is ≥2 or any lymph node size >3 cm.
- Gross total excision of both primary and nodal disease; this includes tonsillectomy,local excision of primary site, and nodal excision that remove all clinically and radiographically evident disease

- Prior radiotherapy to the region of the study cancer that would result in overlap of radiation therapy fields
- Patients with a medical condition or social situation that at the discretion of the PI would preclude them from completion of the trial

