# 4 STUDY DESIGN AND ENDPOINTS

# 4.1 DESCRIPTION OF THE STUDY DESIGN

 $PSI = \frac{V_{diagnosis} \times e^{\lambda \ \Delta t} - V_{treatment}}{V_{diagnosis} \times (e^{\lambda \ \Delta t} - 1)}$ 

- PSI will be calculated according the above formula, where Vdiagnosis is the volume of the tumor at first imaging and Vtreatment is the volume of the tumor at second pretreatment imaging, t is time, and λ is doubling time. Patients with a PSI ≤ 0.75 will be assigned to conventional fractionation group, and PSI > 0.75 will be assigned to the hyperfractionation group (Figure 3).
- Each site of disease (primary and each lymph node) will be independently contoured and PSI calculated for each. PSI of the lymph nodes will take priority over primary site. PSI of the largest lymph node will take priority over smaller lymph nodes.
- Based on PSI, patients will be assigned to one of two cohorts:
- $PSI \leq 0.75$ : Conventional fractionation 2 Gy once daily, Monday through Friday.
- \*\*Should patients be assigned to conventional fractionation, and do not meet the predicted >32% reduction AND they are not receiving concurrent chemotherapy, their treatment will be accelerated via a 6th fraction per week, given as a BID dose once during the week or on a Saturday.
- PSI > 0.75: Hyperfractionation 1.2 Gy twice daily, at least 6 hours apart, Monday through Friday.

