# 6.5 DRUG THERAPY

There will be no concurrent chemotherapy. Other drug therapy (e.g. lidocaine rinses, skin creams, narcotics) as clinically indicated for the management of radiotherapy side effects as per standard of care.

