fBlood samples to be collected at pre-therapy, during treatment at week 2 and week 4, end of treatment, 3 months post-RT, 6 months post-RT, 12 months post-RT, 18 months post-RT, 24 months post-RT, time of diseaseprogression (if sooner than 24 months), and end of study (if patient discontinues the study with any reason sooner than 24 months). See 7.2.4/7.2.5 for collection windows.

gFollowing this visit, patients are considered off the trial and are followed as per standard of care. hPre-treatment CT or MRI for PSI calculation can be up to 180 days prior to CT simulation.

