# 7.4 CONCOMITANT MEDICATIONS, TREATMENTS, AND PROCEDURES

# Not applicable

# 7.5 PROHIBITED MEDICATIONS, TREATMENTS, AND PROCEDURES

Not applicable

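### Partial removal or treatment of the deciding lesion between the two PSI scans biases PSI upward, can carry it past the 0.75 cut, and the plan neither excludes nor handles this

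*Combined protocol and SAP*

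**What the plan says.** **Eligibility.** The surgical exclusion in 5.2 is "Gross total excision of both primary and nodal disease", and it counts tonsillectomy, local excision and nodal excision only when they leave no evident disease: "nodal excision that remove all clinically and radiographically evident disease". Section 5.1 asks for disease at one site or the other: "Patients must have clinically or radiographically evident measurable disease at the primary site or at nodal stations". A patient with one site excised, or one lesion partly removed, can therefore enroll. The only prior treatment excluded in 5.2 is "Prior radiotherapy to the region of the study cancer that would result in overlap of radiation therapy fields". The drug therapy section (6.5) says "There will be no concurrent chemotherapy" and is silent on earlier drug treatment. Section 7.5, on prohibited treatments, is marked as not applicable.

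**Scans.** Section 5.1 requires the scans to be at least one week apart. Section 7.3, footnote h, adds: "Pre-treatment CT or MRI for PSI calculation can be up to 180 days prior to CT simulation". No section requires both scans to fall on the same side of an excision, a debulking biopsy or a drug.

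**PSI and assignment.** Section 4.1 gives the formula, "where Vdiagnosis is the volume of the tumor at first imaging and Vtreatment is the volume of the tumor at second pretreatment imaging", and 7.1 repeats it. PSI is calculated per lesion; nodes outrank the primary and the largest node outranks smaller ones. PSI above 0.75 leads to hyperfractionation, otherwise conventional fractionation. There is no rule for a PSI above 1.

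**The concern.** Section 2.2 defines PSI as tumor volume over carrying capacity and models only logistic growth between irradiations. The formula infers saturation from how little the lesion grew between two scans. Tissue taken out by a surgeon, or lost to a drug, lowers the second volume in the same way as slow growth, and the formula cannot tell them apart.

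The assignment rule is the intervention under test. If PSI is wrong for the lesion that decides, the patient's group may reflect a procedure and not tumor growth. The error runs one way, from conventional fractionation to hyperfractionation. In a single-arm trial of 60 patients with no concurrent control, such patients count as PSI-guided, and no planned analysis separates them.

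**Working it through.** **The plan's own figure.** Section 10.2.1 states about 79% power at a type I error of 0.1. The exact two-stage binomial calculation (49 + 11 patients; stop at 27 or fewer or at 30 or more; final success at 35 or more of 60) gives power 0.7915 at 63% and type I error 0.0928 at 49%. Both agree with the plan, and this point does not alter them.

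**Inputs for PSI**
- Formula and 0.75 cut: 4.1 and 7.1.
- λ = 0.045/day: the only growth rate in the documents, from the lung cancer fit in the Figure 1 legend (2.2). It is an assumption here, with 0.01 to 0.10/day as the range. Section 4.1 calls λ a doubling time, but in the formula it acts as a growth rate.
- True PSI = 0.26: the mean of the preliminary study in 2.2, whose range is 0.03 to 0.75.
- Gap: the minimum is 7 days (5.1); 14, 28 and 60 days are illustrative.

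**Step 1: rearrange.** Let E = exp(λΔt) and r = Vtreatment/Vdiagnosis. Then

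PSI = (E − r)/(E − 1) = 1 − (r − 1)/(E − 1).

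For any positive λ and gap, E − 1 > 0. So r < 1 gives PSI > 1, and r < 1 + 0.25(E − 1) gives PSI > 0.75.

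**Step 2: effect of removal.** Without interference, a lesion with true PSI s has r₀ = 1 + (1 − s)(E − 1). If a fraction f of the volume it would have had at the second scan is removed, r = (1 − f)r₀, and PSI rises by f·r₀/(E − 1). That is positive for every f > 0, so the bias is always upward. The removal needed is

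- to pass 0.75: f = 1 − [1 + 0.25(E − 1)]/r₀
- to pass 1: f = 1 − 1/r₀

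**Step 3: numbers, λ = 0.045/day, s = 0.26**

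| Gap (days) | E − 1 | r₀ = 1 + 0.74(E − 1) | r at the 0.75 cut | f to pass 0.75 | f to pass 1 |
|---|---|---|---|---|---|
| 7 | 0.370 | 1.274 | 1.093 | 14.2% | 21.5% |
| 14 | 0.878 | 1.649 | 1.219 | 26.1% | 39.4% |
| 28 | 2.525 | 2.869 | 1.631 | 43.1% | 65.1% |
| 60 | 13.880 | 11.271 | 4.470 | 60.3% | 91.1% |

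At 14 days, removing 10% gives PSI 0.45 (still conventional), 30% gives 0.82 (hyperfractionation, but below 1) and 50% gives 1.20.

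**Step 4: range.** At 14 days and s = 0.26, the 0.75 cut is crossed at about 7% removal for λ = 0.01/day (1 − 1.038/1.111) and 46% for λ = 0.10/day (1 − 1.764/3.261). With λ = 0.045/day and 14 days, it is crossed at 34% for s = 0.03, 15% for s = 0.50 and 3.5% for s = 0.70. The result that PSI exceeds 1 when r < 1 does not depend on λ.

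**Step 5: lesion hierarchy.** Suppose the primary is wholly removed and the largest node is intact with r = 1.5, at a 14-day gap. The primary's PSI is 1 + 1/0.878 = 2.14, but the node decides with PSI = 1 − 0.5/0.878 = 0.43. The patient stays in conventional fractionation. If the deciding node itself is excised, the text does not say whether its PSI or the next lesion's applies.

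**The case against.** A reader might infer that any tumor removed between the scans forces PSI above 1. It does not. The removal must affect the deciding lesion, must fall between its two scans, and must exceed interval growth to take PSI above 1. Small removals can leave the assignment unchanged. The hierarchy in 4.1 also protects many patients: a subtotal tonsillectomy or a biopsy of the primary changes nothing when an involved node decides, and 5.1 accepts nodal cytology for diagnosis, so a nodal diagnosis need not involve excision. These limits stand.

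The systemic-therapy route is hypothetical. Section 2.3 says the population was chosen because radiotherapy alone is standard for it, and no section anticipates induction treatment. The documents leave the route open, but do not show that anyone takes it. If it were taken, several lesions could shrink together and the hierarchy would protect less.

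It is also tempting to say that the primary endpoint is inflated. Section 4.2.1 measures week-4 response against the simulation or week-1 scan, not against Vdiagnosis, so tissue removed before simulation does not count as response.

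The objection does not remove the gap. Section 5.2 names tonsillectomy, local excision and nodal excision, so the sponsor foresaw these procedures. Node-negative patients are eligible, and their primary decides. For an affected deciding lesion, the stated rule returns a wrong index and not merely an imprecise one.

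**Conclusion.** The point holds within limits. When the deciding lesion is partly removed or treated between its two PSI scans, PSI is biased upward. It can pass 0.75 and exceeds 1 whenever Vtreatment is below Vdiagnosis. The direction and the condition for exceeding 1 are algebra. The removal needed to change the assignment (about 14%, 26% and 43% at 7, 14 and 28 days) rests on λ = 0.045/day from lung cancer and a true PSI of 0.26, and varies widely with both.

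The documents give no count of affected patients; it may be small or zero. They do not support saying that surgery generally sets the fractionation group, that pretreated patients are being enrolled, or that the test's error rates or the response baseline are compromised. What is at stake is whether the result can be read as evidence on PSI-guided assignment for every patient counted. The plan should be changed because the error falls in the rule under test, runs in one direction, and is cheap to prevent.

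**What to change.** 1. In 4.1 and 7.1, state that a lesion's PSI is valid only if no excision, debulking or anticancer drug affected that lesion between its two scans, so that both scans follow the last such event.
2. In 5.1/5.2, make a valid PSI pair for the deciding lesion an eligibility condition.
3. Record any such event with its date relative to both scans. Report the week-4 response rate with and without patients who had one or whose PSI exceeds 1.
4. Reconcile 5.2, footnote h of 7.3, and 4.1/7.1 on how patients with an event between scans are assigned, including when the deciding node was excised and when PSI exceeds 1. No fractionation rule is proposed here.

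Sample size, endpoint and stopping boundaries are unchanged. The cost is that a few patients need a later scan or are screened out. The repeat CT simulation in 7.1 cannot be relied on as the replacement second scan: it falls on the first day of radiotherapy or within 5 days of the start, which may be too late for planning.

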# 5.3 PARTICIPANT WITHDRAWAL OR TERMINATION

Participants are free to withdraw from participation in the study at any time upon request. An investigator may terminate participation in the study in the following circumstances:

- If any clinically adverse event (AE), laboratory abnormality, or other medical condition or situation occurs such that continued participation in the study would not be in the best interests of the participant
- If the participant meets an exclusion criterion (either newly developed or not previously recognized) that precludes further study participation.

## 5.4 PREMATURE TERMINATION OR SUSPENSION OF STUDY

This study may be temporarily suspended or prematurely terminated if there is sufficient reasonable cause. Written notification, documenting the reason for study suspension or termination, will be provided by the suspending or terminating party to investigators and regulatory authorities. If the study is prematurely terminated or suspended, the PI will promptly inform the IRB and will provide the reason(s) for the termination or suspension.

Circumstances that may warrant termination or suspension include, but are not limited to:

- Determination of unexpected, significant, or unacceptable risk to participants
- Demonstration of efficacy that would warrant stopping
- Insufficient compliance to protocol requirements
- Data that are not sufficiently complete and/or evaluable
- Determination of futility

Study may resume once concerns about safety, protocol compliance, data quality are addressed.

# 6 STUDY AGENT

Not applicable.

#### 6.1 DOSING AND ADMINISTRATION

Based on PSI, patients will be assigned to one of two cohorts:

1. Conventional fractionation – 2 Gy once daily, Monday through Friday.

	All disease ≤ 2	Any site of	Any site of
	cm	disease > 2 cm but ≤ 4 cm	disease > 4 cm
Gross	60 Gy / 30	66 Gy / 33	70 Gy / 35
Disease	fractions	fractions	fractions
Elective	41.4 Gy / 23	41.4 Gy / 23	41.4 Gy / 23
Nodes	fractions	fractions	fractions

\*\*Should patients be assigned to conventional fractionation, and do not meet the predicted >32% reduction AND they are not receiving concurrent chemotherapy, their treatment will be accelerated via a 6th fraction per week (as per standard of care which is one twice daily fraction per week, > 6 hours apart OR on the weekend).

2. Hyperfractionation – 1.2 Gy twice daily, at least 6 hours apart, Monday through Friday.

	All disease ≤ 2 cm	Any site of disease > 2 cm but ≤ 4 cm	Any site of disease > 4 cm
Gross	60 Gy / 50	64.8 Gy / 54	69.6 Gy / 58
Disease	fractions	fractions	fractions
Elective	41.4 / 36	41.4 / 36	41.4 / 36
Nodes	fractions	fractions	fractions

#### 6.2 TREATMENT PLANNING/TARGET VOLUMES

The treatment plan used for each patient will be based on an analysis of the volumetric dose, including dose-volume histogram analyses of the planning target volume (PTV) and critical normal structures.

Gross tumor volume (GTV) represents the region judged to contain gross primary tumor or involved node(s) based on clinical and endoscopic examinations, CT scan, MRI, and PET-CT.

Clinical target volumes (CTV) are defined and contoured in relation to the targets that they are intended to encompass and the dose they are intended to receive. For gross targets (GTVs), the CTVs are defined by 3D isotropic expansions of 0.5 cm that should then be limited by potential barriers to tumor spread such as air cavities, external contours, and bony or fascial planes through which tumor spread is not possible or apparent.

Elective clinical target volume consists of elective nodal basins at risk depending on size and location of the primary site and grossly involved nodes. In general this consists of levels 2-4 and potentially retrostyloid and retropharyngeal ipsilaterally, and levels 2-3 contralaterally. If tonsil primary without involvement (or <1 cm involvement) of base of tongue or soft palate, unilateral elective neck radiotherapy may be delivered. This will be at the discretion of the treating radiation oncologist.

PTV represents an additional margin around the GTV to compensate for the variability of treatment set up and internal organ motion. The CTVs will be expanded symmetrically 2.5 to 3 mm to generate the PTV.

## **Detailed Organs at Risk Specifications**

SpinalCord: The cord begins at the foramen magnum. Superior to this is brainstem and inferior to this is cord. The inferior border of the spinal cord volume will be defined at approximately the carina (ie, 2-3 cm below the lowest slice level that has PTV on it). The spinal cord shall be defined based on the treatment planning CT scan.

SpinalCord\_PRV05: Planning Risk Volume (PRV) spinal cord defined as SpinalCord + 5 mm in all directions.

BrainStem: The inferior most portion of the brainstem is at the cranial-cervical junction where it meets the spinal cord. For the purposes of this study, the superior most portion of the brainstem is approximately at the level of the top of the posterior clinoid. The brainstem shall be defined based on the treatment planning CT scan.

BrainStem\_PRV03: Planning Risk Volume (PRV) brainstem defined as Brainstem + 3 mm in all directions.

Parotid\_R/L: Parotid glands will be defined in their entirety (superficial and deep lobes) based on the treatment planning CT scan.

Pharynx: This will be defined as superior/middle/inferior constrictor muscles. This extends from the superior constrictor region (level of the inferior pterygoid plates) to the cricopharyngeal inlet (level of the posterior cricoid cartilage).

Esophagus\_UP: This will be defined as the cervical or superior (S) esophagus, a tubular structure that starts at the bottom of pharynx (cricopharyngeal inlet) and extends to the thoracic inlet.

Larynx: This will be defined as the glottic and supraglottic larynx, including the tip of the epiglottis, the epiglottis, the aryepiglottic folds, arytenoids, false cords, and true cords, up to but not including the medial border of the thyroid cartilage, and including the cricoid cartilage to the inferior edge of the arytenoid cartilage, but not the hypopharynx.

OralCavity: The oral cavity will be defined as a composite structure consisting of the lips, oral tongue/floor of mouth, buccal mucosa, and superiorly the palate, and inferiorly to the plane containing the tip of the mandible.

Submandibula\_R/L: Submandibular glands will be defined in their entirety based on treatment planning CT scan.

Mandible: This includes the entire bony structure of the mandible from TMJ through the symphysis.

Thyroid: Thyroid gland should be contoured in its entirety based on treatment planning CT scan.

The density-corrected dose distributions shall be calculated, and the dose prescription will be based on a dose distribution corrected for heterogeneities.

Dosimetry: Intensity-modulated RT, volumetric modulated arc therapy, or tomotherapy planning is acceptable. Typically,  $\geq$  7 beams or  $\geq$  2 arcs of radiation will be used.

Prescription Isodose Surface Coverage: The prescription isodose surface will be chosen such that  $\geq$  95% of the PTV is conformally covered by the dose and 100% of the PTV would be covered with the isodose surface that is represented by 95% of the prescription dose. 100% of the GTV should be covered by 100% of the prescription dose.

High Dose Spillage: Any dose  $\geq$  105% of the prescription dose should occur primarily within the PTV itself and not within the normal tissues outside the PTV. Therefore, the cumulative volume of all tissue outside the PTV receiving a dose > 105% of the prescription dose should be no more than 0.03 cc of the PTV volume.

Prioritization for Intensity-Modulated RT Planning:

- 1. Spinal cord
- 2. Brainstem
- 3. Gross target PTV
- 4. Elective PTV
- 5. Organs at Risk
  - a. Parotid gland contralateral to primary tumor site
  - b. Larynx
  - c. Pharynx
  - d. Contralateral submandibular gland
  - e. Oral Cavity/Lips
  - g. Esophagus
  - h. Parotid gland ipsilateral to primary tumor site
  - i. Mandible
- 6. Unspecified tissue outside the targets

# 6.3 DOSES TO NORMAL STRUCTURE

Dose limitations to normal structures are described below. For the critical structures of spinal cord and brainstem, these are mandatory. For other structures, recommended limits are provided, but the doses delivered should always be as low as reasonably achievable without compromising doses to PTVs.

- **Spinal cord:** The planning risk volume (PRV) (Spinal cord + 0.5 cm) for spinal cord should not exceed 48 Gy to any volume in excess of 0.03 cm^3 (approximately 3 mm x 3 mm x 3 mm).
- **Brain stem:** The PRV for (brainstem + 0.3 cm) brainstem should not exceed 50 Gy to any volume in excess of 0.03 cm^3 (approximately 3 mm x 3 mm x 3 mm). In treatment planning, the brain stem\_03 should be given less priority than the spinal cord, but more than the critical structures listed below.
- **Oral cavity/Lips:** Reduce the dose as much as possible. The mean dose should be <32 Gy for the oral cavity. Efforts should also be made to avoid hot spots (> 60 Gy) within the non-involved oral cavity.
- **Parotid glands:** The treatment planning goal will be for this individual parotid gland to receive a mean dose of < 26 Gy, but efforts should be made to reduce this further if possible without compromising dose to PTVs.

- **Contralateral submandibular gland:** If contralateral level lb is not a target, aim to reduce mean contralateral submandibular gland to < 39 Gy.
- **Pharynx:** Reduce the dose as much as possible. Mean pharynx dose recommended to be <50 Gy.
- **Esophagus:** Reduce the dose as much as possible; recommended (not mandatory) treatment goal: mean dose < 30 Gy.
- Larynx: Reduce the dose as much as possible. The larynx mean dose is recommended to be ≤ 35 Gy if whole-neck *i*ntensity-modulated RT is used.
- **Mandible:** Reduce the dose as much as possible. Hot spots within the mandible should be avoided. It is recommended that maximum dose within the mandible be < 105% of prescription dose.
- Unspecified tissue outside the targets (Non-PTV): No more than 1 cm^3 of unspecified tissue outside the targets can receive ≥ 105% of the prescription dose.

